10.1.2 Toxicity

10.1.2.1 Preclinical studies

In a GLP toxicology study, 4 Cynomolgus monkeys received 20 $\mu\text{g}/\text{Kg}$ days 1, 3 and 5 with no significant toxicity. Another four monkeys were then given 300 $\mu\text{g}/\text{Kg}$ days 1, 3 and 5 and experienced dose-limiting toxicity with anorexia and 2 to 4-fold transaminase elevations. The

Abbreviated Title: LMB-2 for HCL
Version date: 02/07/2023

LD10 and LD50 in mice were 200 and 257 µg/Kg every other day for 3 doses. The cause of death was liver damage.

10.1.2.2 Phase I and II trials

Adverse events were reported in relationship to treatment cycle. Grade III-IV toxicities included reversible transaminase elevation, fever, CK elevation, cardiomyopathy, thrombocytopenia, allergic reaction, and diarrhea.

The most common grade I-II toxicities were transaminase elevation, fever, hypoalbuminemia, and fatigue. Other grade I-II toxicities included vascular leak syndrome/capillary leak syndrome, weight gain, hypotension, nausea, pericardial effusion, allergy, proteinuria, and increased creatinine.

10.2 PREMEDICATIONS (ABBREVIATED PHARMACEUTICAL SECTION)

These agents will be provided by the Clinical Center Pharmacy and will be given orally. Please refer to the package inserts for complete pharmaceutical information on these products.

10.2.1 Acetaminophen (Tylenol):

- Side effects are extremely unlikely. Regular use of acetaminophen can cause liver damage especially at high doses (>4000 mg/day or >12 regular strength tablets per day). To minimize this possibility patients should not take over-the-counter products containing acetaminophen during the time periods they are taking scheduled acetaminophen doses on this study.

10.2.2 Ranitidine (Zantac):

- Side effects include tiredness, dizziness, headache, and diarrhea.

10.2.3 Hydroxyzine (Atarax):

- Side effects include sleepiness, dizziness, restlessness, and irritability.

10.2.4 Dexamethasone (Decadron):

- To be given only prior to the 1st dose of retreatment cycles. Side effects of a single dose of dexamethasone might include difficulty sleeping, increased hunger, and increased blood glucose. Steroids are associated with an increased risk of infection although this is more applicable to chronic use.

11 CORRELATIVE/SPECIAL STUDIES

Note: tubes and media for research tests may be substituted based on availability with the permission of the PI or laboratory investigator.

11.1 ASSAY FOR DETECTING NEUTRALIZING ANTIBODIES TO LMB-2.

- 11.1.1 Set up SP2/Tac cell plates using SP2/Tac cell line protocols. Place cell plates in 37°C incubator until needed.
- 11.1.2 Using a costar #3799 U-bottom plate, add 72 ul of .2% PBS/HSA to wells A1-A4 and 60 ul to wells A9-A-12. Add patient serum, obtained from serum separator or other clot tube, to the plate in the following manner:
 - a. Patient 1: 45 ul of serum in wells D1-D4
 - b. Patient 2: 45 ul of serum in wells E1-E4
 - c. Patient 3: 45 ul of serum in wells F1-F4
 - d. Patient 4: 45 ul of serum in wells G1-G4
 - e. Patient 5: 45 ul of serum in wells H1-H4
- 11.1.3 Thaw LMB-2 toxin in hand and add 15 ul to well A12. Mix well. Transfer 15 ul from well A12 to well A11. Mix well. Transfer 15 ul from well A11 to well A10. Mix well. Well A9 does not receive toxin.
- 11.1.4 Using a multichannel pipette, transfer 8 ul from wells A9-A12 into wells A1-A4. Well A1 receives from well A9, well A2 from well A10, etc.
- 11.1.5 In a similar manner, transfer 5 ul from wells A9-A12 into the patient serum wells. For example, well D1 receives from well A9, etc. Dispel pipette tips between additions to patients samples.
- 11.1.6 Using a multichannel pipette, mix wells A1-A4, and all patient sample wells in which toxin additions were made. Dispel pipette tips between each set.
- 11.1.7 Incubate the U-bottom plate at 37°C for 15 minutes.
- 11.1.8 During incubation, prepare two new Costar #3799 U-bottom plates with 200 uL of room temperature SP2/Tac cell media in all used rows.
- 11.1.9 Add 10 uL of .2% PBS/HSA to row C of U-bottom plate #2.
- 11.1.10 When the 15 minute incubation of plate one is complete, add from plate one to plate two in the following manner:

Using a single channel pipette:

Transfer 10 ul from plate 1, well A1 to plate 2, wells A1-A6.
Transfer 10 ul from plate 1, well A2 to plate 2, wells A7-A12.
Transfer 10 ul from plate 1, well A3 to plate 2, wells B1-B6.
Transfer 10 ul from plate 1, well A4 to plate 2, wells B7-B12.

Using a multichannel pipette:

Transfer, in triplicate, 10 ul from patients wells of plate 1 into the corresponding wells of plate two. For example, patient #1 sample from well D1 of plate one is transferred to wells D1-D3 of plate two. Patient #1 sample from well D2 is added to wells D4-D6 of plate two, etc. Continue to add samples in this manner until all Patient samples have been added to plate 2.

11.1.11 After transfers are complete, mix all wells of plate two using a multichannel pipette. Be sure to dispense tips between rows.

11.1.12 Using a 12-tip multichannel pipette, make direct transfers of 18.5 ul from plate 2 into plate 3 by row. For example, transfer wells A1-A12 of plate 2 into wells A1-A12 of plate 3. Mix plate 3 using a multichannel pipette as explained previously.

11.1.13 As in step 12, make a direct transfer of 50 ul from plate 3 into the cell plates prepared before start of assay. Gently add dilution to the cell plate (do not pipette up and down).

11.1.14 Incubate the SP2/Tac assay plates 18-20 hours at 37°C. Pulse the cell plates using leucine-free RPMI media and 3H leucine at a dilution of 1:50 (1 uCi/well). Gently add 50 ul of the 1:50 {¹²⁵I}-leucine dilution to the assay plates using a multichannel pipette. Dispense tips between rows. Incubate the plates for 41/2 hours at 37°C.

11.1.15 The cell plates are harvested after incubation using a MACH III Tomtek cell harvester. Harvester instructions located in protocol book in room 428A. The cells are harvested onto filter mats and read using a Wallac Beta Counter and the data is electronically captured.

Reasons to repeat an assay:

1. Failure to get counts above 2500.
2. Failure of the standard curve.
3. Low counts in serum only tube (as compared to subsequent serum dilutions).
4. PI requests a repeat of assay.

11.2 BIOASSAY FOR BLOOD LEVELS OF LMB-2

11.2.1 Plate SP2/Tac cells at 40,000/well in flat bottom plates. A typical PK assay requires 3 plates (I, II, and III).

11.2.2 Label 2 U-bottom plates (I & II) and add room temperature SP2/Tac media in the following fashion:

a. In U-bottom plate I: wells A1-A5 receive 200 ul, wells A6-A7 receive 198 ul/well, A8 receives 205 ul, columns 1-3 starting with row B receive 198 ul, and column 4 receives 205 ul starting with row B.

b. In U-bottom plate II: wells A1-4 and A7-10 receive 200 ul of media, columns 1-3 and 7-9 starting with row B receive 198 ul, and columns 4 and 10 starting with row B receive 205 ul.

- 11.2.3 Add 8.5 ul of each plasma time point to column 4 starting with row B of U-bottom plate I in sequential order. It is very important to double-check the order of the time points. Day 1 time points are added first in order of time drawn, then day 3, etc. A total of seven time points can be added to U-bottom plate I.
- 11.2.4 Proceed to U-bottom plate II. Additional time points, in sequential order, can be added first to column 4 starting with row B, then to column 10 also starting with row B. Row A is left blank in both U-bottom plates as Row A is used for the titration row. [name] HSA requested a total of two “blank” rows per PK assay. These rows receive only media in the final step of the assay (no toxin or plasma is added to these rows). The assay must be structured so that a total of two rows in the flat bottom plates are not used. A total of 19 time points can be run on three plates. If more than 19 time points are to be run, it will be necessary to use an additional cell plate IV.
- 11.2.5 After the plasma samples are added to the U-bottom plates, an 8 well multichannel pipette is used to the dilutions. The same procedure is used on each U-bottom plate starting with row B. Transfer 22 ul from column 4 into column 3 (i.e. 22 ul from B4 is transferred into B3, etc.). Column 3 is mixed well and 22 ul is transferred from column 3 into column 2. Finally, 22 ul is transferred from column 2 into column 1. The same procedure is used to make dilutions from column 10 through column 7 of U-bottom plate II. It is important that thorough mixing is performed after each dilution and before the next transfer is made.
- 11.2.6 Add 8.5 ul of LMB-2 toxin to well A8 of U-bottom plate I. Mix well. Transfer 22 ul of A8 into A7, 22 ul of A7 into A6, 50 ul of A6 into A5, 50 ul of A5 into A4, 50 ul of A4 into A3, 50 ul of A3 into A2, and 50 ul of A2 into A1. Again, thorough mixing is necessary in each well before each transfer is made.
- 11.2.7 Transfer 50 ul from well A5 of U-bottom plate I into wells A4 and A10 of U-bottom plate II. A series of 50 ul transfers are made from A4 to A3, from A3 to A2, and from A2 to A1 with thorough mixing after transfer. Next, 50 ul transfers are made from A10 to A9, from A9 to A8, and from A8 to A7. This is to assure a titration curve for each of the three cell plates of the PK assay. Once the toxin is added to the U-bottom plates and mixed, the final transfer to the cell plate is made. At this point, there should be three sets of four columns containing serum and toxin dilutions on the U-bottom plates I and II.
- 11.2.8 The PK assay does not require a 15 minute incubation before addition of samples to the cell plates. Therefore, a multichannel pipette is used to transfer a 50 ul aliquot from each column of the U-bottom plates to the SP2/Tac cell plates in triplicate. For example, 50 ul from column 1 of U-bottom plate I is added to columns 1-3 of SP2/Tac cell plate I, column 2 of U-bottom plate I is added to 4-6 of cell plate I, column 3 to columns 7-9, and column 4 to columns 10-12 etc.
- 11.2.9 Similarly, 50 ul from columns 1-4 of U-bottom plate II are transferred to SP2/Tac cell plate II in triplicate and columns 7-10 of U-bottom plate II are added to SP2/Tac cell plate III in triplicate. Remember to add 50 ul of media (without toxin or plasma) to the

Abbreviated Title: LMB-2 for HCL

Version date: 02/07/2023

rows used as blank rows. If media is not added to these rows, the counts will be slightly higher and will not accurately represent the control value.

11.2.10 Incubate the plates for 18-20 hours at 37°C. End of DAY 1.

11.2.11 DAY 2

Following overnight incubation at 37°C, the plates are pulsed, harvested, and counted as in the neutralization assay.

Reasons to repeat assay:

1. Failure to get counts above 2500.
2. Failure of standard curve.
3. Draw points run in improper order.
4. Repeat requested by [name].

11.2.12 Follow Up

For follow-up studies in patients off-treatment, which will not affect eligibility for enrollment or retreatment, a non-radioactive neutralization assay may be used, under non-CLIA conditions. For additional correlation between the 2 assays, serum samples are saved to enable the new assay to be run with historical samples previously tested using the radioactive CLIA assay..

12 STUDY CALENDAR

Procedures	Eligibility Evaluation		Every Treatment Cycle										Post-Treatment	
	Prior to Cycle 1	Pre-cycle	Day 1	Day 2	Day 3	Day 4	Day 5	Day 6	Days 7-8	Week 2	Week 3	Week 4	8 weeks after CR ⁶	Every 3-12 months ⁵
Blood sample for CD25 analysis (by FACS)	X	X												X
History (include PS) & physical exam	X	X												
Echocardiogram, stress test	X													
ECG, CXR	X	X												
CT scan of chest/abdomen/pelvis or abdominal MRI ¹	X												X	X
Serum anti-LMB-2 antibody assay, HIV, Hep BsAg & C	X													
Pregnancy test if applicable	X													
Bone Marrow Biopsy	X												X	
Drug administration (LMB-2)			X		X		X							
CBC/diff	X	X			X		X			X	X			X
Acute care panel, hepatic panel, mineral panel	X ³	X			X		X			X ³	X ³			
Total protein	X													
LDH, PT, Beta-2 microglobulin (B2M), SPEP, urinalysis	X													
LDH, urinalysis, uric acid, CK		X			X		X							
Fibrinogen, D-dimer, uric acid, amylase, lipase, IgG, IgA, IgM, CRP, ferritin, haptoglobin, B2M and SPEP		X												
PT, PTT		X												
24 hour Urine for CrCl	X	X												
Pharmacokinetic Studies ²			X		X		X							
Neutralizing antibodies and soluble Tac		X									X ⁴			X ⁷

Abbreviated Title: LMB-2 for HCL

Version date: 02/07/2023

¹ A CT scan (in patients with an abnormal initial scan) will be done routinely after even cycle numbers (2, 4, 6) and will be done at other times if there is clinical evidence that the patient has had a PR, CR, or progressive disease. Ultrasound can replace CT/MRI in the absence of lymph nodes, at the discretion of the PI.

² Refer to Section [4.3](#) for PK collection instructions and schedule.

³ Albumin is collected instead of mineral panel.

⁴ Between Days 17-25.

⁵ Refer to Section [4.10](#).

⁶ Refer to Section [4.4.3](#).

⁷ Only for patients with PD

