2.5 DOSE DETERMINATION

The MTD established in the phase I trial of LMB-2 in 12 patients was 40 ug/Kg QOD x3. In phase II testing, Four out of 5 patients with CLL tolerated this dose level without DLT, and one patient with CTCL had grade IV CPK elevation without other evidence of DLT. This led to a lowering of the phase II dose level in the CTCL trial to 30 ug/Kg QOD x3. Because HCL is more like CLL in having an intravascular component, we plan to use the 40 ug/Kg QOD x3 dose level. LMB-2 will be given every 4 weeks for up to 6 cycles.

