3 ELIGIBILITY ASSESSMENT AND ENROLLMENT

3.1 ELIGIBILITY CRITERIA

3.1.1 Inclusion Criteria

3.1.1.1 Histopathological evidence of CD25+ HCL confirmed by the NIH pathology department. This will require a monoclonal population of peripheral malignant lymphocytes that are CD25 positive by fluorescence activated cell sorting (FACS) with anti-CD25 antibody. Positive expression in a FACS assay is defined as more than 2 times the mean fluorescence intensity (MFI) of the control antibody by FACS. HCLv (HCL variant) is usually CD25 negative, and eligibility would require CD25+ HCLv.

3.1.1.2 At least one of the following indications for treatment: neutropenia (ANC <1000 cells/ul), anemia (Hgb <10g/dL), thrombocytopenia (Plt <100,000/ul), an absolute lymphocyte count of >20,000 cells/ul or symptomatic splenomegaly.

3.1.1.3 Previous treatment with or inability to receive BL22 or HA22 recombinant immunotoxin. Patients must have had at least 2 prior systemic therapies, including 2 courses of a purine nucleoside analog (PNA), or 1 course of either rituximab or BRAF inhibitor following a single prior course of PNA.

3.1.1.4 ECOG performance status of 0 – 2.

3.1.1.5 At least 18 years old.

3.1.1.6 Understand and give informed consent.

3.1.1.7 A negative pregnancy test in female patients of childbearing potential. Women must not be breast-feeding (see section [5.1.1.1](#)).

3.1.1.8 ALT and AST \leq 5-times the upper limits of normal. Albumin \geq 3.0 gm/dL. Total bilirubin \leq 2.2 mg/dL.

3.1.1.9 Creatinine \leq 1.4 mg/dL or creatinine clearance \geq 50 ml/min.

3.1.1.10 Serum that neutralizes \leq 75% of the activity of 1 μ g/mL of LMB-2 using a bioassay.

3.1.1.11 No systemic cytotoxic chemotherapy within 4 weeks of enrollment or systemic steroids (except stable doses of Prednisone \leq 20 mg/day, or up to 4 doses of steroid given for non-therapy reasons) within 4 weeks of enrollment.

3.1.1.12 No anti-CD25 monoclonal antibody therapy within 12 weeks of enrollment.

3.1.1.13 No prior treatment with LMB-2.

3.1.1.14 Patients may not be receiving any other investigational agents.

3.1.1.15 Patients should not have uncontrolled intercurrent illness including, but not limited to, symptomatic congestive heart failure, unstable angina pectoris, cardiac arrhythmia, or psychiatric illness/social situations that would limit compliance with study requirements.

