3.2 RESEARCH ELIGIBILITY EVALUATION

- A blood sample will be submitted to the NIH pathology department for analysis of CD25 expression (an eligibility criterion) by FACS analysis. This analysis will be done in the Laboratory of Pathology, NIH (Anatomic Pathology Dept., CC), a College of American Pathologists (CAP) and CLIA-approved laboratory, by standardized diagnostic techniques.
- Complete history and physical examination with documentation of measurable disease (lymph nodes, spleen, liver), stage, and performance status within 2 weeks before starting LMB-2. Physical examination should record the diameter, in two planes, of the largest palpable nodes in each of the following sites: cervical, axillary, supraclavicular, inguinal, and femoral. Physical examination should record liver and spleen size as determined by measurement below the respective costal margin.

- ECG and CXR within 3 days before starting LMB-2.
- CT scan of the chest, abdomen, and pelvis, or abdominal MRI, within 4 weeks before starting LMB-2.
- Serum anti-LMB-2 antibody assay, HIV, Hepatitis B surface antigen, and hepatitis C screen within 2 months before starting LMB-2.
- Laboratory evaluation within 2 weeks before starting LMB-2 will include CBC/differential, acute care panel (electrolytes, glucose, BUN, creatinine), hepatic panel (AST, ALT, Alkaline phosphatase, total and direct bilirubin), albumin, LDH, PT, Beta 2 microglobulin (B2M), serum protein electrophoresis (SPEP), urinalysis, and a 24 urine creatinine clearance and total protein. A CBC/differential, acute care panel, hepatic panel, and albumin must be done within 3 days of starting cycle 1.
- Urine or serum pregnancy test within 72 hours before starting LMB-2 in women with childbearing potential.
- Bone marrow biopsies and echocardiogram with left ventricular ejection fraction calculation, and stress test, will be done on all patients within 2 months before starting LMB-2.

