4 STUDY IMPLEMENTATION

4.1 STUDY DESIGN

This is a Phase II study to test the response of patients with HCL to LMB-2. LMB-2 will be given every 28 days (minimum of 25 days) for up to 6 cycles. No patient whose serum neutralizes > 75% of the activity of 1 µg/mL of LMB-2 will be retreated. In patients who

achieve a CR with minimal residual disease (MRD), defined as positive immunohistochemistry of bone marrow biopsy or flow cytometry of blood, no more than 4 additional cycles of LMB-2 will be administered. Patients with CR without MRD may receive 2 additional cycles. Patients who relapse after >2 months of a CR or PR are eligible for retreatment with LMB-2 alone on the same schedule if they still meet initial eligibility criteria and were not removed from study due to toxicity, provided that the study is still open and the LMB-2 supply permitting. Stopping rules in this case will be the same as those during initial LMB-2 administration. Patients will be treated with LMB-2 as described below. Response and duration of response will be determined as described in section [13](#).

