5.1.1 Justification for Exclusions

Patients with hepatitis C positivity are excluded from this trial because of the concern that LMB-2 may worsen hepatitis C. Patients with hepatitis B are not excluded if on Lamivudine, which is used to prevent reactivation/worsening of hepatitis B with chemotherapy and other immunosuppressive treatments. Patients that are pregnant or breast-feeding will be excluded from this trial because the effect of LMB-2 on the developing fetus or the nursing infant is unknown and potentially harmful.

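### No pregnancy test is scheduled after cycle 1, so in a six-cycle course five later cycles (15 of 18 doses) can start untested in a woman of childbearing potential.

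*Combined protocol and SAP*

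**What the plan says.** Entry requires "A negative pregnancy test in female patients of childbearing potential" (3.1.1.7). Section 3.2, the eligibility evaluation, sets the timing: "Urine or serum pregnancy test within 72 hours before starting LMB-2 in women with childbearing potential". The calendar in section 12 repeats this in the row "Pregnancy test if applicable", with one mark under *Prior to Cycle 1*. The row is empty under *Pre-cycle*, in every day and week of the treatment cycle, and after treatment.

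The reason for excluding pregnant or breast-feeding patients is in 5.1.1: "because the effect of LMB-2 on the developing fetus or the nursing infant is unknown and potentially harmful".

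Treatment then continues for months. Section 4.1 states that "LMB-2 will be given every 28 days (minimum of 25 days) for up to 6 cycles", and 2.5 gives the same limit: "LMB-2 will be given every 4 weeks for up to 6 cycles". Each cycle is three doses (4.2). For a complete response with minimal residual disease (MRD), 4.1 adds that "no more than 4 additional cycles of LMB-2 will be administered"; without MRD, two more cycles are allowed. Patients who relapse after a response lasting more than two months may be treated again "if they still meet initial eligibility criteria".

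**The concern.** A negative test shortly before cycle 1 says nothing about conception afterwards. The reason the plan gives for excluding pregnancy applies with equal force at cycle 2 or cycle 6, but no test or dosing condition carries it forward. The plan handles another changeable entry criterion differently: neutralizing antibodies are tested before each cycle (4.7), and a patient who exceeds the limit comes off therapy (4.9.1).

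What is at stake is fetal exposure to an immunotoxin in a woman who does not yet know she is pregnant. It is a safety-schedule matter. The response endpoint and the two-stage design do not depend on it.

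**Working it through.** The plan states no figure of its own on this point. The check is a reading of every rule that governs later cycles, followed by a count.

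**Rules that could require a later test or stop dosing**

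- 4.4.1, laboratory tests on or within 3 days before day 1 of each cycle: long list, no pregnancy test.
- 4.4.2, tests during each cycle: none.
- 4.2.4, recovery before the next cycle: toxicities and blood counts only.
- 4.7, conditions for further cycles: no progression and insufficient neutralizing antibodies to bar treatment.
- 4.9.1, removal from therapy: eight criteria, none of them pregnancy. The off-treatment list in 6.2.1 does not include it either.
- 4.1, retreatment after relapse: the entry criteria apply again, which implies a new test at that point. The rule does not reach the later cycles within a course.

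The text and the calendar agree, so the blank cells in the calendar are not an artefact of table extraction.

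**Count for a full six-cycle course**

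Inputs: 6 cycles and a 25 to 28 day interval (4.1); 3 doses per cycle (4.2); one test, before cycle 1 (3.2 and section 12).

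- Total doses = 6 × 3 = 18.
- Cycles with no scheduled test = 6 − 1 = 5.
- Doses in those cycles = 5 × 3 = 15, and 15 / 18 = 83%.
- First day of cycle 1 to first day of cycle 6 = 5 × 25 = 125 days to 5 × 28 = 140 days. It is longer if cycles are delayed, because 4.1 sets only a minimum interval and 6.3 permits delays.

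**If consolidation extends the course**

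The plan does not settle whether consolidation cycles count within the six. Section 13.2 schedules scans after cycles 2, 4, 6, 8 and 10, which suggests they are additional. Calendar footnote 1 lists only 2, 4 and 6, and 2.5 says up to 6, which suggests they are not.

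| Reading | Cycles | Untested cycles | Doses in them | Days, first to last cycle start |
|---|---|---|---|---|
| Consolidation within six | 6 | 5 | 15 | 125–140 |
| Added after response at cycle 6, no MRD | 8 | 7 | 7 × 3 = 21 | 7 × 25 to 7 × 28 = 175–196 |
| Added after response at cycle 6, with MRD | 10 | 9 | 9 × 3 = 27 | 9 × 25 to 9 × 28 = 225–252 |

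None of these is an absolute ceiling, since 4.7 allows more cycles with prior FDA approval.

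**With a test before every cycle**, the count of cycles started without a scheduled test falls from 5 of 6 to 0 of 6.

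**The case against.** The strongest reply is that the plan contradicts nothing. The entry criterion, the timing in 3.2 and the calendar all agree, and repeat testing is added practice. That is right, and the point is put as a missing safeguard.

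Second, other provisions cover part of the risk. A history and physical examination precede every cycle (4.4.1), and the team discusses each patient under treatment at least weekly (8.4). The wording in 5.1.1 that pregnant patients are excluded from the trial is not expressly limited to entry, so a recognised pregnancy might well end treatment. This narrows the gap to an unrecognised pregnancy that begins between cycles. None of these provisions is a test for that.

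Third, contraception or pregnancy-notification wording may stand in pages not available for this review, such as the consent form. This cannot be ruled out, and it would lower the risk. It would not be a scheduled test or a condition for dosing.

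Fourth, the 15 doses measure the schedule and not harm. They assume that all six cycles are given, and neutralizing antibodies, toxicity or progression will shorten many courses. The plan gives no age or sex distribution and no expected number of cycles, so the effect across the trial cannot be estimated. All of this stands, and it is why the point is minor.

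**Conclusion.** The point holds as a low-priority safety improvement. With the plan followed exactly, a woman of childbearing potential in a six-cycle course starts 5 cycles (15 of 18 doses) without a scheduled pregnancy test, the last of them nominally 125 to 140 days after cycle 1. Under the longer reading of consolidation, the count is 7 or 9 cycles.

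The count assumes a completed course and the absence of a further testing rule in pages not seen. The number of women concerned is unknown, probably small, and possibly zero: the trial aims for at most 25 evaluable patients, although its accrual ceiling of 55 also covers inevaluable participants and screen failures (15.2), and some inevaluable participants could have been dosed. The primary response analysis is unaffected.

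**What to change.** For women of childbearing potential:

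1. Section 12: mark the pregnancy test in the *Pre-cycle* column.
2. Section 4.4.1: add it to the tests done within 3 days before day 1. This matches the 72-hour window already used at entry.
3. Section 4.7: require a negative result before each cycle is dosed. If the result is positive, hold LMB-2 and confirm with a repeat test.
4. Section 4.9.1: add confirmed pregnancy as a reason for removal from protocol therapy.

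While editing, correct the cross-reference in 3.1.1.7 to a section 5.1.1.1; no heading with that number appears in the text, and 5.1.1 carries the relevant content.

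The cost is one inexpensive assay per later cycle, 5 per woman in a six-cycle course, on blood or urine already collected before each cycle. No extra visit is needed, and neither the endpoint nor the sample size changes. The one drawback is that a false positive could delay a cycle until the repeat test is back.
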